3.1 Study Design

This will be a 3 week, randomized, single-center, double-blind, proof-of-concept (POC) pilot study to evaluate the efficacy of patients with mild-moderate COVID-19+ infection. There will be an initial 10-pateint open-label study to assess patient tolerance to the active treatment arm of the study. The first 10 open-label patients will be treated with BSS 2 tablets PO (to chew) up to 4 times daily for 3 days (72 hours). The second 2 groups of patients will be mild (at home) or moderate (hospitalized, not on a ventilator) COV+ testing or with persistently + COVID testing for 14 days or more.

Patients will be allowed to receive a SOC treatment regimen at baseline (Appendix 2)

Standard of care (which includes any non-excluded SOC medications).

This pilot study will be conducted in the US in 1 center. A total of 60 patients are expected to be enrolled into the 3 arms of the study. Study one will consist of 10 open label COV+ patients with mild/moderate disease, the second and third studies will be double-blind placebo controlled studies of 25 patients each, the first with Mild/Moderate disease upon diagnosis by QRT-PCR+ testing and the third will consist of patients who are COV+, mild to moderate in severity with documented COV+ status by QRT-PCR testing for 14 days or more.

Screening will occur at the time patients are diagnosed via QRT-PCR testing. This may occur at one of several locations and/or time points of diagnosis:

- emergency room [ER]
- physician's office on the U of L campus.
- · University of Louisville hospitals (ULH Main and Jewish facilities).
- · Selected parking lot on UL campus.

 Campus Health (patients/students may be recruited via Practitioners or by approved recruitment flyers

Patients with initial COV+ confirmed by QRT-PCR testing will be approached to provide informed consent for the study. A third group of patients will be recruited with persistently + QRT-PCR testing for 14 days or more (see table 2).

Randomization will occur during SOC treatment.

Visits will occur at Baseline (Day 1) when patients will receive their first dose of study drug (BSS or PBO), and daily during the study until the patient tests COV- by saliva test or 21 days, whichever comes first.

The study design is depicted in Appendix 2.

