3.2 Selection of Study Population

3.2.1 Inclusion Criteria

To be eligible to participate in the study, patients must meet the following criteria:

- Ability to provide written or remote informed consent (telephone and DocuSign)
- Ability to comply with study requirements,
- Men or women 18 to 85 years of age, inclusive
- Current diagnosis of an initial occurrence of non-severe, non-complicated COV+ infection as defined by:
 - Presence COVID-19 in the saliva or nasal cavity using POC QRT-PCR assay or, in study #3, documented COV+ status for 14 days or more.
 - Management in an outpatient (i.e., non-hospital) or inpatient setting NOT on a ventilator.
 - Alert and awake
 - · Able to chew the study drug completely.
 - Women should fulfill one of the following criteria:
 - Answer in the affirmative that "they are not or could not be pregnant"
 - Post-menopausal; either amenorrhea ≥12 months or follicle stimulating hormone >20 mIU/mL
 - Surgically sterile; hysterectomy, bilateral oophorectomy, or tubal ligation.
 - Women of childbearing potential participating in heterosexual sexual relations must be willing to use adequate contraception from Screening through the 21 Day visit, per Section 10.2.

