3.6. Statistical Methods

3.6.1 Statistical Analysis Plan

Statistical Analysis Plan

Efficacy Analysis:

The primary efficacy analyses will be to compare the negative Saliva rates at Week 1, 2 and 3 between the SOC control group and the BSS + SOC treatment groups using the analysis of variance (ANOVA) with treatment group and baseline BMI as a covariate variable in the model. Clinical factors such as age, antibiotic use, number of recurrences, etc. will be examined for the impact on the treatment effect.

The analyses of the primary efficacy endpoint will be conducted to compare historical SOC control vs. BSS plus SOC groups. The ANOVA or a nonparametric method, whichever is appropriate, will be used to compare the rates of recurrence at each time point.

For categorical endpoints, chi-square test or a Fisher exact test (for 2x2 tables) will be used to assess treatment effect. For continuous endpoints, the ANOVA or a nonparametric method will be used, whichever is appropriate.

The comparability of patient's population at baseline will be assessed using either chisquare test (for categorical data) or t-test (for continuous variables).

Safety Analysis:

Intent-to-treat (ITT) patients who receive one dose of study drug will be included in the safety evaluation.

The number of AEs reported by patients, who participate in the study, as well as their causality and severity, will be summarized for each treatment group. Frequency tables for AEs by MedDRA terms will be presented. AEs will be assessed by age, sex, and race.

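### Section 3.6.1 lists number of recurrences, which cannot vary under the inclusion criteria, leaves antibiotic use undated, and does not name the protocol's own split between home and hospital patients

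*Combined protocol and SAP*

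**What the plan says.** Section 3.6.1 (Efficacy Analysis) specifies for the saliva-negative rates an "analysis of variance (ANOVA) with treatment group and baseline BMI as a covariate variable in the model". It then adds: "Clinical factors such as age, antibiotic use, number of recurrences, etc. will be examined for the impact on the treatment effect". Later in the section recurrence also appears as an outcome, to be used to "compare the rates of recurrence at each time point".

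Section 3.2.1 admits patients with a "Current diagnosis of an initial occurrence of non-severe, non-complicated COV+ infection as defined by" a set of conditions. One of these covers the persistent-positive patients ("in study #3, documented COV+ status for 14 days or more"); another is "Management in an outpatient (i.e., non-hospital) or inpatient setting NOT on a ventilator".

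Section 3.1 describes the patients of the two blinded studies as "mild (at home) or moderate (hospitalized, not on a ventilator". Sections 3.1 and 3.4.1.3 run visits and saliva testing until the first negative test or Day 21.

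Section 3.5.2 gives 20 BSS and 5 placebo patients in each blinded study. Section 3.5.1 assigns by coin toss or another suitable method and mentions no stratification.

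**The concern.** The plan spends one of its few named factors on a quantity that the eligibility rules hold constant. It leaves a second factor undated, so that it may be measured after randomisation. The one entry characteristic that the protocol itself uses to separate mild from moderate disease goes unnamed.

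Care setting is a natural candidate for adjustment. It is fixed at entry, it is the protocol's own marker of severity, and it bears directly on a secondary objective, the duration of hospitalisation. In a trial with so few placebo patients, the arms can easily differ in their mix of home and hospital patients by chance. The analysis as written has no stated way to account for that, and the open wording leaves the choice until after the data are seen.

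**Working it through.** The plan gives no power, effect size or imbalance figure to reproduce. The stated total, 10 + 25 + 25 = 60, is consistent.

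**1. Can number of recurrences be examined?**
- Before entry: 3.2.1 requires an initial occurrence. The persistent-positive study falls under the same criterion, and 14 days or more of positive tests is persistence, not recurrence. The count is the same for every eligible patient.
- On study: testing stops at the first negative saliva test, so no recurrence after clearance would be seen. If one were seen, it would be a post-randomisation event and not a baseline modifier.
- In the model: take the columns intercept, treatment, recurrences and treatment × recurrences for 20 BSS and 5 placebo patients. With recurrences constant at 0, the last two columns are zero. With recurrences constant at 1, they duplicate the first two. The rank is 2 of 4 either way, and a larger N does not change this.

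**2. When is antibiotic use measured?** Section 3.4.1.1 collects medication history for the previous 30 days, and 3.4.1.3 updates it during the study. Section 3.6.1 does not say which is meant, so either reading is open.

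**3. Where does care setting appear?** Section 3.6.1 names treatment and baseline BMI in the model, and age, antibiotic use and recurrences as factors. The only severity it mentions is that of adverse events. The baseline comparability variables are not listed.

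**4. How likely is chance imbalance?**
Inputs: 5 placebo of 25 per cohort, or 10 of 50 pooled (3.5.2). The hospitalised share is not in the documents, and 40% is assumed first. With K hospitalised of N, n on placebo and k of those hospitalised:
- P(k) = C(K,k)·C(N−K,n−k)/C(N,n)
- gap = |k/n − (K−k)/(N−n)|

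Per cohort (N = 25, n = 5, K = 10; C(25,5) = 53,130):

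| k on placebo | gap (points) | allocations |
|---|---|---|
| 0 | 50 | 3,003 |
| 1 | 25 | 13,650 |
| 2 | 0 | 20,475 |
| 3 | 25 | 12,600 |
| 4 | 50 | 3,150 |
| 5 | 75 | 252 |

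- P(gap ≥ 25) = 1 − 20,475/53,130 = 61%.
- P(gap ≥ 35) = (3,003 + 3,150 + 252)/53,130 = 6,405/53,130 = 12%.

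Pooled (N = 50, n = 10, K = 20): the gap is below 25 points only for k = 3, 4 or 5.
- P(gap ≥ 25) = 1 − (0.2259 + 0.2801 + 0.2151) = 28%.
- P(gap ≥ 35), from k = 0, 1 or 7 and above, is 7%.

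Other assumed shares, from the same formula:
- Pooled, gap ≥ 25: 5% with 10% hospitalised, 18% with 20%, 25% with 30%, 29% with 50%.
- Per cohort, gap ≥ 25: 28% with 8 of 25 hospitalised (15,050/53,130) and 32% with 12 of 25 (17,094/53,130). In these two cases no possible gap lies between 25 and 35 points, so the same figures hold for a gap of 35 or more.

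**5. Could care setting be a formal subgroup instead?** Let m be the moderate share.
- The chance that all 5 placebo patients of a cohort fall in one setting, so that the interaction cannot be estimated, is m⁵ + (1−m)⁵: 6.3% at m = 50%, 17.1% at 30% or 70%, 32.8% at 20% or 80%.
- With expected cell sizes, the interaction standard error is 1/√(m(1−m)) times the main-effect standard error: 2.0, 2.18 and 2.5 times respectively.

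A formal subgroup test is not supportable at this size.

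**The case against.** Several stronger readings are tempting, and the documents do not support them.

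- *Severity is shut out of the analysis.* It is unnamed, not excluded. The factor list is open-ended, the factors are to be examined rather than formally tested, and the baseline comparison could include care setting.
- *Care setting determines opiate access, COVID-19 therapy and who counts stools.* Sections 3.2.2 and 3.5.5 also allow opiates in outpatients when prescribed. Standard COVID-19 therapy is permitted without reference to setting. Stool frequency is recorded daily for all patients in the same way.
- *The antibiotic factor breaks the randomised comparison.* The text is ambiguous, and a baseline reading is available from the 30-day history. That calls for clarification and does not prove an error.
- *The imbalance figures show bias.* Chance imbalance is not systematic bias, and no figure in the documents links setting to stool frequency or viral clearance.

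The magnitude is also fairly open to challenge. In a 20:5 cohort with 10 hospitalised, the possible gaps are only 0, 25, 50 and 75 points, so any threshold just above 25 takes 61% to 12%. Recruitment on campus and in physicians' offices makes a low hospitalised share plausible. The figures rest on the 20:5 split. A coin toss giving 25:25 overall would cut the pooled 28% to 4%, and the documents do not reconcile the toss with 20:5.

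Finally, the choice of covariates in a small pilot is partly discretionary. That is so, but it does not rescue a factor that cannot vary, and it is no reason to leave the choice open until the data are in.

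**Conclusion.** The point holds in a limited form. Number of recurrences cannot be examined in this population; that follows from the eligibility and follow-up rules and needs no assumption. The timing of antibiotic use is undefined. Care setting is known for every patient at entry and is named in no model, factor list or stratum.

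The size of the imbalance risk depends on an assumed hospitalised share and on the 20:5 allocation. At 40% hospitalised, a gap of at least 25 points has probability 61% per cohort and 28% pooled, and a gap of at least 35 points has 12% and 7%. Across assumed shares of 10% to 50%, the pooled 25-point figure runs from 5% to 29%. These are probabilities of imbalance in setting, not estimates of error in the treatment effect. The gain from adjustment is precision and protection of this one small trial's estimate. The omission does not invalidate the trial, but it is worth correcting before the data are seen.

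**What to change.** In 3.6.1:

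- Delete number of recurrences from the factor list, and close the list.
- Limit antibiotic use to use before Day 1.
- Add Day 1 care setting (at home or hospitalised) as a covariate in the efficacy comparisons that use a model. The section writes out a model only for saliva-negative rates, so state that the covariate also applies to the stool-frequency comparison.
- Show results by care setting descriptively only, with no interaction test.
- Check the sentence on rates of recurrence at the same time: no recurrence endpoint stands among the objectives (section 2) or the efficacy assessments (3.4.2).

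The cost is SAP wording and one degree of freedom. No new data are needed and N does not change. With intercept, treatment and BMI already in the model, residual degrees of freedom fall from 47 to 46 if the 50 blinded patients are pooled, and from 22 to 21 if each 25-patient study is analysed separately. The cost weighs more in the separate analyses, where only 5 patients are on placebo. The plan should say which analysis is intended.

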3.4.1.3 Daily Visits (1+/-21 Days)

The visits may occur daily up to Day 21(whichever comes first), or until the patient tests COVID- by saliva test. The following procedures will be performed at this visit:

- a. Medication history updated to include any changes or new medications since baseline;
- b. Recording of daily stool frequency and symptom questionnaire;
- c. Patient daily testing by saliva sample for COVID-19
- d. Assessment of AEs;
- e. Stool specimen collection at Day 7, Day 14 and Day 21. Collection kits to be given to patient 1 day prior if in an outpatient setting.

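### Section 3.6.1 names two conflicting primary analyses; neither matches the primary objective, and one of them, rates of recurrence, cannot be estimated from the planned follow-up

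*Combined protocol and SAP*

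**What the plan says.** The Efficacy Analysis text in section 3.6.1 opens with one primary analysis: "The primary efficacy analyses will be to compare the negative Saliva rates at Week 1, 2 and 3", between an SOC control group and BSS plus SOC.

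The following paragraph starts again: "The analyses of the primary efficacy endpoint will be conducted to compare historical SOC control vs. BSS plus SOC groups". Its only named outcome comes in the next sentence, where ANOVA or a nonparametric method "will be used to compare the rates of recurrence at each time point". Recurrence also appears among the covariates to be explored: "Clinical factors such as age, antibiotic use, number of recurrences, etc".

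Elsewhere the protocol reads differently:

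- **Section 2** makes mean daily stool frequency, BSS against placebo, the primary efficacy objective. Time to viral clearance by daily saliva test is secondary.
- **Section 3.4.2** lists stool frequency, time to negative test and adverse events as efficacy assessments. Recurrence is not listed.
- **Section 3.1** schedules visits "daily during the study until the patient tests COV- by saliva test or 21 days, whichever comes first". Section 3.4.1.3 repeats the rule for the daily visits at which saliva is tested: "or until the patient tests COVID- by saliva test".
- **Section 3.2.1** requires "Current diagnosis of an initial occurrence of non-severe, non-complicated COV+ infection".

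**The concern.** Recurrence means clearance followed by a return of infection, so measuring it needs testing after clearance. The design ends scheduled testing at clearance. The outcome named in the primary-endpoint paragraph is therefore one that the trial does not systematically collect.

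That alone could be corrected by striking a phrase. It matters more because of what surrounds it. The SAP's other primary analysis (saliva-negative rates) is not the protocol's primary objective either, and section 3.6.1 names no analysis of stool frequency as primary. No sentence says which statement governs. A primary result is interpretable as confirmatory only if the outcome was fixed in advance. Here an analyst could report any of the three and point to text in support.

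**Working it through.** The documents give no recurrence rate, effect size, alpha or power, so there is no stated figure to reproduce. The check compares the outcome with the observation window.

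**1. Candidate primary outcomes**

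| Place | Outcome | Comparator | Estimable as designed? |
|---|---|---|---|
| Section 2 | Mean daily stool frequency | Placebo | Yes, once the averaging window is stated |
| 3.6.1, first paragraph | Saliva-negative rate at Weeks 1, 2, 3 | SOC control | Yes, if a patient who stopped on a negative test counts as negative afterwards |
| 3.6.1, second paragraph | Recurrence rate at each time point | Historical SOC control | No |

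The second row works only by carrying the first negative forward, which assumes that nobody recurs. The third row needs the opposite: data on what happens after that negative.

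**2. Scheduled saliva tests after the first negative**

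Let T be the day of the first negative test. Daily visits end on day min(T, 21).

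- If T ≤ 21, the last scheduled test is on day T, so tests after T = T − T = 0.
- If T > 21, the patient has not cleared within the study and cannot have recurred in it.

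Either way the count is 0, whatever the distribution of T. This applies to all 25 + 25 = 50 randomised patients. A recurrence rate at Week 1, 2 or 3 has no systematically observed patients at risk.

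**3. How much post-clearance time the stop rule removes (illustration)**

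The documents give no clearance time. Assume exponential clearance with median m days, rounded up to whole days.

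- Share cleared before Day 21 = 1 − 2^(−20/m).
- Mean post-negative days per patient if all were followed to Day 21 (patients not cleared count as 0) = Σ over k = 1 to 20 of (1 − 2^(−k/m)).

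| Assumed median m | Cleared before Day 21 | Mean post-negative days if followed | Under the stop rule |
|---|---|---|---|
| 5 | 94% | 13.7 | 0 |
| 7 | 86% | 11.7 | 0 |
| 10 | 75% | 9.6 | 0 |
| 14 | 63% | 7.6 | 0 |

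The conclusion in step 2 does not depend on these assumptions.

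**4. Number of recurrences as a factor**

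Eligibility asks for an initial occurrence, and the third group consists of persistently positive patients, not recurrent ones. The protocol does not say what would be counted, or over what period, so the factor has no clear meaning.

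**The case against.** Four points deserve weight.

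**The SAP has another primary analysis.** A reader might infer that the trial has no primary analysis that can be run. The documents do not support that: saliva-negative rates can be derived under the stop rule. What cannot be done is one of two conflicting descriptions.

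**Some post-negative tests could occur.** A reader might infer that recurrence can never be observed. That is too strong. Appendix 1 marks saliva testing at unscheduled visits and in the Day 7 and Day 14 columns, and no footnote limits these to patients still positive. A positive after a negative could be recorded. But no trigger is described and sections 3.1 and 3.4.1.3 provide no systematic follow-up, so such results would be haphazard and would not yield a rate by time point.

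**The covariate is not shown to be zero for everyone.** The wording on initial occurrence invites that inference. However, the listed defining criteria ask only for a positive test or, in the third group, 14 days or more of positivity. None checks for earlier infection. The supportable criticism is that the factor is undefined. As one example in an open-ended exploratory list, it has little consequence.

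**The wording may be carried over from another protocol.** That is plausible but cannot be established from the documents, and it would not help. The phrase still names the outcome in the primary-endpoint paragraph.

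These points narrow the claim. None supplies a definition of recurrence, a schedule for measuring it, or a rule for choosing among the three outcomes.

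**Conclusion.** The point holds, and section 3.6.1 is wrong as written. It contains two conflicting primary analyses, neither of which is the primary objective in section 2. The recurrence analysis cannot be estimated, because recurrence is undefined and the stop rule leaves 0 scheduled saliva tests after a first negative for any of the 50 randomised patients.

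This rests on two readings: that recurrence means a return of SARS-CoV-2 positivity after clearance, which the documents never state, and that sections 3.1 and 3.4.1.3 govern testing where Appendix 1 is silent.

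It would go too far to infer that the replacement outcome will be picked after seeing the data. Two workable alternatives are already written down. The risk is that the choice between them could be made afterwards, because nothing in the documents settles it.

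**What to change.** In section 3.6.1:

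1. Delete the reference to rates of recurrence and the reference to number of recurrences.
2. Before unblinding, state one primary analysis that matches section 2: mean daily stool frequency, BSS versus concurrent randomised placebo. Remove the historical control from the primary comparison.
3. State the days over which the mean is taken. Stool frequency is recorded at the same daily visits, so it too stops at the first negative test.
4. Make time to negative saliva test secondary, as in sections 2 and 3.4.2.

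The cost is SAP wording only, with no new visits, samples or patients.

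If the sponsor does want recurrence, it must be defined and saliva testing scheduled after the first negative for everyone. That is a design change with little return at this size. Taking the 20 BSS to 5 placebo split in section 3.5.2, and assuming recurrence of 30% on placebo and 10% on BSS (not in the documents), exact power of a two-sided 0.05 Fisher test is about 16% within one group (5 versus 20) and 34% with both pooled (10 versus 40).

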Two specific papers have supported the use of Bismuth as a treatment option for COV+. [name] (Hong Kong) found that Bismuth was effective in inhibiting the SARS Corona virus helicase. Of note, this potential efficacy was noted by the Jinyintan Hospital during the current COV-19 pandemic. After several of their staff were infected, they used bismuth compounds prophylactically and noted no further infections.

These data point to the efficacy of preventing viral enteritis and low risk-profile for patients treated with BSS. Clearly, BSS may be part of a strategy for COV+ treatment given its low therapeutic risk profile and documented gut-virus clinical efficacy.

2. Study Objectives

The objectives of this pilot study are: To evaluate the tolerance and efficacy of BSS and SOC in mild/moderate severity COV+ population as defined by QRT-PCR of saliva or nasal swab samples compared to SOC and placebo and compare this efficacy to patients treated with SOC (placebo) alone. This will first be tested in 10 open-label patients, then in 2 groups of 25 patients as follows: Group one with mild/moderate disease and Group 2, patients with mild/moderate disease and persistently positive

for the SARS-Cov-2 virus by QRT-PCR testing for 14 days or more. This study is to assess the potential for BSS to influence the gut as a reservoir of infection by the SARS-Cov-2 virus and to determine the primary effect objective of change in stool frequency of patients treated with BSS compared to placebo treated patients.

Primary efficacy objective:

To determine whether treatment with BSS of Mild/Moderate COV+ decreases mean daily stool frequency compared to placebo-controlled patients

Secondary efficacy objectives:

Duration of hospitalization in BSS compared to PBO treated groups.

Weight gain (and BMI) relative to baseline at Week 1, and through Week 2.

Stool microbiota at baseline and Week 1, and through Week 2 (to be analysed at a later date).

To determine whether treatment with BSS of Mild/Moderate COV+ decreases the time to viral clearance (negative test by daily saliva testing) and persistently COV+ testing patients (over 14 days of COV+ testing) with Mild/Moderate disease, time until negative test by daily Saliva test.

3. Investigational Plan

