3.4.1.1 Screening Visit (Days -1 to 0)

Screening will occur at the time the diagnosis of COV+ is confirmed for the first study. For the second study, screening will occur at 2 weeks or more of documented COV+ status. During the screening visit

enrolled patients will be provided with a stool collection kit. Two patient groups will be studied: The following will be obtained to determine patient eligibility:

- a. Written or remote informed consent; (telephone and DocuSign)
- b. Demographic data;
- c. Medication history for the previous 30 days;
- d. Medical history including daily stool frequency;
- e. Social history (alcohol, tobacco, drugs);
- f. Height and Weight (which can be self-reported);
- g. Vital signs (temperature, pulse, blood oxygen saturation, blood pressure within 1 week of screening visit);
- h. Verbal affirmation that to the best of their knowledge they are not pregnant;
- i. Collection of serious, procedure-related non-treatment emergent AEs;
- Reminder for patients to avoid the use of protocol excluded medications for the duration of the study

All screening laboratory test results must be reviewed, signed, and dated by an Investigator when they are received (see list in Appendix 2).

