3.4.1.2 Baseline Visit/Dosing (Day 1)

The baseline visit should occur within 2 days after the screening assessment. The following procedures will be performed at this visit:

- Medical and medication history update to include any changes or new medications since screening if applicable, and to ensure there is no change in medical condition that, in the Investigator's opinion, would interfere with study participation;
- b. Weight (which can be self reported);
- c. Recording of vital signs (temperature, pulse, blood oxygen saturation);
- d. Patient daily testing by saliva sample for COVID-19; Note: These data will not be reconciled with clinical data collected during the study. Saliva collection protocol:
 - a. The patient should not consume food or drink within 30 mins of sample collection
 - ID number placed on 15 ml collection tube and source docs so all samples/data can be reconciled.
 - Provide patient with sterile 15 ml falcon tube, ethanol wipe, and paper-covered straw.
 - d. The patient uses the straw to funnel spit into the collection tube. At least 1 ml of saliva should be collected. NOTE: saliva can be foamy, the foam does not count towards the 1 ml. Saliva collection may be undertaken inside the car with the window up.
 - e. Patient screws lid onto the tube, wipes down outside with ethanol wipe, and places into biohazard bag held by site personnel. The patient keeps straw and wipe and disposes of in the trash.
- Stool sample for bacterial speciation, metabolomics (at a later date). Collection kits will be provided at initial screening.
- f. Collection of serious, study procedure-related, nontreatment-emergent AEs;
- Review dosing instructions with the patient and stress the importance of compliance;
- h. Schedule all daily study visits.
- i. Recording of daily stool frequency and symptom questionnaire.

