3.4.2 Efficacy Assessments

- Mean daily stool frequency and aggregate weekly stool frequency of treated versus placebo treated patients
- Time to negative test of subjects experiencing clinical cure (negative test of saliva-confirmed COV+infection).
- Incidence of Adverse Events (AEs)

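### The SAP specifies no baseline adjustment for stool frequency, the primary objective, although pre-treatment stool frequency is collected; ANCOVA would be a cheap gain in precision

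*Combined protocol and SAP*

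**What the plan says.** Section 2 (Study Objectives) states the primary efficacy objective as whether BSS "decreases mean daily stool frequency compared to placebo-controlled patients". Earlier in the same section the objective is worded as a change in stool frequency against placebo, with no reference point for the change. Section 3.4.2 lists "Mean daily stool frequency and aggregate weekly stool frequency of treated versus placebo treated patients" among the efficacy assessments, without calling any of them primary.

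Stool frequency is collected before treatment. Section 3.4.1.1 item d obtains "Medical history including daily stool frequency", and Appendix 1 marks daily stool frequency at screening. Section 3.4.1.2 item i adds "Recording of daily stool frequency and symptom questionnaire" on Day 1. Section 3.1 makes Day 1 the day of the first dose, and neither section says whether the Day 1 record comes before it.

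Section 3.6.1 does not mention stool frequency. Its one named baseline covariate, BMI, belongs to the model for negative saliva rates. Stool frequency falls under the general sentence "For continuous endpoints, the ANOVA or a nonparametric method will be used, whichever is appropriate". The SAP also plans baseline comparability tests and an open-ended look at clinical factors. Neither names stool frequency.

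On size, Section 3.1 says "the second and third studies will be double-blind placebo controlled studies of 25 patients each". The table in Section 3.5.2 splits each cohort 20 BSS to 5 placebo, whereas Section 3.5.1 assigns by coin toss.

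**The concern.** With 25 patients per blinded cohort, and as few as 5 on placebo, precision is scarce. A patient's stool frequency before treatment is a natural predictor of stool frequency on treatment, and it is already being collected. If the primary-objective comparison does not use it, the confidence interval is likely to be wider than the data allow. Leaving the covariate open also leaves the choice of model to be made after the data are seen.

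**Working it through.** **Inputs.** From the documents: 25 patients per blinded cohort (Section 3.1); 20:5 per cohort (Section 3.5.2), or about 13:12 if the coin toss governs (Section 3.5.1). The plan gives no SD, correlation, alpha or power, so there is no figure of its own to reproduce. Assumed: baseline-outcome correlation r = 0.3, 0.5 or 0.7; SD 1 to 2 stools/day; two-sided 95% intervals.

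**1. Unadjusted half-width, 20:5, in SD units.** t(23 df) × sqrt(1/20 + 1/5) = 2.069 × 0.5 = 1.034. The sample SD averages about 1 − 1/(4 × 23) = 0.989 of the true SD, so the expected half-width is 1.034 × 0.989 = 1.02.

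**2. Adjusted half-width, 20:5, r = 0.5.** ANCOVA multiplies the residual SD by sqrt(1 − r²) = 0.866 and costs one degree of freedom: 2.074 × 0.5 × 0.866 = 0.898. The sample-SD factor 1 − 1/(4 × 22) = 0.989 gives 0.888. Chance baseline imbalance inflates the variance by about 1 + 1/21 on average, so the half-width is about 0.888 × 1.02 = 0.91.

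**3. Simulation** (4,000 runs per setting, normal data, cohort in the model when combined). Change in mean 95% CI half-width when baseline is added:

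| Allocation | r = 0 | r = 0.3 | r = 0.5 | r = 0.7 |
|---|---|---|---|---|
| One cohort, 20:5 | +2.5% | −2.1% | −11.1% | −26.5% |
| One cohort, 13:12 | +2.5% | −2.4% | −11.2% | −27.0% |
| Combined, 40:10 | +1.1% | −3.5% | −12.3% | −27.8% |
| Combined, 25:25 | +1.2% | −3.5% | −12.5% | −27.6% |

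At 20:5 and r = 0.5 the simulated half-widths are 1.021 and 0.908 SD, matching steps 1 and 2. The large-sample ceiling, 1 − sqrt(1 − r²), is 5/13/29%.

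**4. In stools/day, r = 0.5.** At SD 1.5: 1.53 to 1.36 (20:5), 1.23 to 1.09 (13:12), 1.06 to 0.93 (40:10), 0.85 to 0.75 (25:25). At 20:5 with SD 1 the fall is 1.02 to 0.91; with SD 2 it is 2 × 1.021 = 2.04 to 2 × 0.908 = 1.82.

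**5. In patients, 20:5.** Net of the lost degree of freedom and chance imbalance, the equivalent sample-size factor is 1/(0.979²), 1/(0.889²) and 1/(0.735²), or about 4%, 27% and 85% more patients at r = 0.3, 0.5 and 0.7.

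**6. Against an unadjusted change score.** Its variance is proportional to 2(1 − r); ANCOVA's is proportional to 1 − r². The CI ratio is sqrt((1 + r)/2) = 0.806/0.866/0.922, so ANCOVA is about 19/13/8% narrower before the lost degree of freedom.

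**7. Break-even.** The r = 0 penalty is a factor of 1.025 (one cohort) or 1.011 (combined). Setting 1.025 × sqrt(1 − r²) = 1 gives r = sqrt(1 − 1/1.025²) = 0.22. The combined case gives sqrt(1 − 1/1.011²) = 0.15.

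**8. Skewed counts.** With lognormal-Poisson data (mean about 3/day, averaged over 7 or 14 days, 6,000 runs, including 20:5), ANCOVA's type I error was 4.4–5.3%. The CI was 11–12% narrower at correlations of 0.46–0.48.

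**The case against.** - **The SAP does not rule out covariates.** It uses ANOVA for the saliva model that contains BMI, so the same word in the general line cannot be read as excluding adjustment. This stands: the covariate is unspecified, not forbidden. The open list of clinical factors could also take in stool frequency, but it prespecifies no adjusted model.
- **The change wording in Section 2 may already use baseline.** If it means change from baseline, the 2/11/27% figures have the wrong comparator and the 19/13/8% figures apply. No reference point is given, so both sets are shown. ANCOVA is narrower in each, apart from the small cost at low correlation.
- **The correlation may be low.** The screening value is a medical-history item and may reflect usual habit rather than the current illness. Below about r = 0.22 in one cohort the adjustment loses slightly.
- **Larger questions come first.** Section 3.6.1 names negative saliva rates as primary and a historical comparator, which conflicts with Section 2. Daily visits also stop at the first negative saliva test, so the averaging window varies by patient. The skewed-count check used fixed windows and does not cover this. Both are separate matters, and the wording below does not define the window. Once stool frequency is analysed as Section 2 asks, it still needs a model.
- **This is a pilot.** A half-width of 1.36 stools/day at 20:5 (SD 1.5, r = 0.5) is still wide. This limits the point to minor.

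**Conclusion.** The point holds as a cheap improvement of minor severity. The SAP leaves the model for the primary objective unspecified, and a collected pre-treatment value would probably sharpen it. At assumed correlations of 0.3/0.5/0.7 the CI is about 2/11/27% narrower than unadjusted in one cohort and 4/12/28% combined, or about 19/13/8% narrower than a change score before the lost degree of freedom. The size rests on the correlation, which the documents do not give.

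A reader might infer more in two ways, and the documents support neither. One is that omitting the covariate biases the comparison. BSS and placebo are randomized in both blinded cohorts, so chance baseline imbalance is noise that the standard error covers. The other is that permitted opiate use (Sections 3.2.2 and 3.5.5) distorts the result and needs its own covariate or table. The same argument from randomization applies to opiate use at baseline, and a table would change no result.

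**What to change.** Add to Section 3.6.1:

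> Mean daily stool frequency will be compared between BSS and concurrent randomized placebo by ANCOVA with treatment and baseline stool frequency as covariate. Baseline is the screening value (3.4.1.1 d) for all patients; the pre-dose Day 1 value is used only if the screening value is missing. If the two blinded cohorts are combined, cohort is added. Historical controls are not used for this endpoint.

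The order of precedence matters because both values may exist and the Day 1 record may follow the first dose. The last sentence matters because the SAP's primary-endpoint text compares with historical standard of care, while Section 2 asks for placebo. Whether to combine the cohorts stays with the sponsor.

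The cost is a short SAP addition and one degree of freedom, with no new visits, patients or data items. The worst case is the r = 0 penalty already shown: about 2.5% on the CI in one cohort, or 1.1% combined. The change should be made before unblinding.
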